7.0 Risks

The primary endpoint of our study is measurement of ventricular arrhythmias (ectopy). This is an expected outcome of our exercise protocol. Risk of adverse clinical consequences of increased ventricular arrhythmias will be reduced by continuation of the participant's medical therapy of AV nodal blockers (Betablockers or calcium channel blockers). Patients with CPVT frequently undergo exercise stress testing as part of routine monitoring. All patients included in our study have successfully completed a minimum of two exercise stress tests with no adverse events. Unexpected findings are cardiac arrest, ICD shock, or death and other unanticipated risks could exist.

Risks associated with Atropine include proarrhythmia, however, based on our preliminary data we expect atropine to reduce ventricular arrhythmias with exercise in patients with CPVT. To manage the risk of proarrhythmia, participants will be observed with continuous cardiac monitoring for 20 minutes following ETT, or until ventricular ectopy has returned to baseline (whichever is longer).

8.0 Reporting of Adverse Events or Unanticipated Problems involving Risk to Participants or Others

Reporting of Adverse Events or Unanticipated Problems involving Risk to Participants or Others:

Definitions of adverse events: an adverse event (AE) is any untoward medical occurrence in a patient or clinical investigation subject administered a pharmaceutical product and which does not necessarily have a causal relationship with the treatment or study protocol.

Adverse events include:

- Worsening (change in nature, severity or frequency) of conditions present at the onset of the trial
- o Patient / subject deterioration due to the primary illness
- o Intercurrent illnesses
- o Drug interactions
- Events related or possibly related to concomitant medications
- Abnormal laboratory values or changes of vital signs, as well as significant shifts from baseline within the range of normal, which the Investigator considers clinically significant.

Unexpected Adverse Drug Reaction: an unexpected Adverse Drug Reaction is an adverse reaction, the nature or severity of which is not consistent with the applicable product information. Definitions of serious adverse events or serious adverse drug reaction: during clinical investigations, adverse events may occur which, if suspected to be drug-related (adverse drug reactions), must be significant enough to lead to important changes in the way the medicinal product is developed (e.g., change in dose, population, needed monitoring, consent forms). This is particularly true for reactions, which, in their most severe forms, threaten life or function.

A serious adverse event/experience (SAE) or reaction is any untoward medical occurrence that:

- 1. results in death
- 2. is life-threatening
- 3. requires inpatient hospitalization or prolongation of existing hospitalization
- 4. results in persistent or significant disability/ incapacity (as per reporter's opinion)
- 5. is a congenital anomaly/birth defect
- 6. is another medically important condition
- 7. The term "life-threatening" in the definition of "serious" refers to an event in which the patient is at risk of death at the time of the event; it does not refer to an event which hypothetically might have caused death if it were more severe.

Important medical conditions that may not result in death, be life-threatening, or require hospitalization may be considered as SAEs when, based upon appropriate medical judgment, they may jeopardize the patient or may require intervention to prevent one of the outcomes listed in the definition above. Examples of such events are intensive treatment in an emergency room or at home for allergic bronchospasm; blood dyscrasias or convulsions that do not result in hospitalization; or development of drug dependency or drug abuse.

Definition of severity of adverse events:

- Mild: Causing no limitation of usual activities; the subject / patient may experience slight discomfort.
- Moderate: Causing some limitation of usual activities; the subject / patient may experience annoying discomfort.
- Severe: Causing inability to carry out usual activities; the subject / patient may experience intolerable comfort or pain.

Protocol Version #: 7 Protocol Date: 6/28/2016 Definition of adverse event causality:

The Investigator will determine causality of each adverse event by using the classification criteria: unlikely, likely, or not assessable.

- *Unlikely:* The AE is considered by the Investigator to be due to a pre-existing condition, a known manifestation of the target disease, a recurrent condition, or is likely explained by environmental or diagnostic therapeutic factors or was pre-existing and did not deteriorate.
- *Likely:* The AE occurred during or after administration of the study treatment or a pre-existing event worsened within an appropriate period of time, and at least one of the following criteria is applicable:
 - the event could not be explained by the clinical condition or history of the subject, environmental or toxic factors, or other diagnostic or therapeutic measure;
 - o was an expected ADR associated with study treatment or a class-labeled drug effect;
 - o AE subsided or disappeared after withdrawal or dose reduction of study treatment; or
 - AE recurred after re-exposure to study treatment.
- *Not assessable:* There is insufficient or conflicting evidence for classifying the causality of the AE as likely or unlikely. Lack of information may apply for this situation.

Note: AEs with causality 'likely' or 'not assessable' are considered to be 'possibly drug-related.'

Adverse event reporting

Any adverse events (AEs) will be reported to the PI within 72 hours of notification of the event. The PI will notify the IRB of any major adverse events. Any unanticipated problems involving risk to the participants or others will be discussed with the PI and IRB. Non-serious AEs and incidences of noncompliance with the protocol will be reported to the IRB at the time of annual review.

Serious Adverse Events (SAEs) will be reported according to the following procedure:

The occurrence of serious adverse events will be reported to the Investigator within 24 hours after notification of their occurrence. The Investigator will report SAEs to the Vanderbilt Institutional Review Board within 7 days of the Investigator's notification of the event.

In an unanticipated event of prolonged side effect, requiring prolongation of hospital stay, patients will be retained in the hospital until side effects have resolved. For minor side effects, where inpatient care is deemed unnecessary, follow- up will be maintained via phone or as outpatient if necessary. Patient and their families will be given the PI's contact number for reporting any other effects of medication following discharge.

Any newly discovered information which may affect the subject or their caregiver's decision to continue to participate in the study will be passed on to them as soon as possible. This may also result in a change to the consent form and review by the IRB.

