6.0 Study Procedures

General Approach: This is a prospective cross-over trial that will enroll eligible patients with CPVT and perform a baseline treadmill exercise tolerance test (ETT) followed by a repeat treadmill ETT with I.V. atropine administered immediately prior to exercise. Atropine is a parasympathetic blocker and results in sinus tachycardia, which is expected to reduce the diastolic interval thereby reducing delayed after depolarizations and ventricular ectopy compared to baseline. Both ETTs will be performed on the same day with two hours of rest scheduled between ETTs. The primary analysis will be a paired comparison of the number of ventricular ectopic beats recorded during exercise (and recovery) at baseline and following pre-treatment with atropine. Secondary endpoints will include the presence of ventricular ectopy (yes/no), complex ventricular ectopy (couplets or greater, yes/no), and the number of runs of complex ventricular ectopy.

Prior to Enrollment	Patient recruited in clinic or by phone
	Patient will continue all outpatient medications prior to study. Specifically, beta-blocker therapy will not be stopped for this study.
Day 1	
8:00 AM	Arrive to Clinical Research Center (CRC)
	Sign consent forms
8:15 AM	Place peripheral I.V.

8:30 AM	Interrogate Device (ICD) (if ICD present)
0100741	Reprogram therapy detection zones if needed
8:45 AM	Place electrodes for ETT
0110741	
Part 1	Baseline Exercise Tolerance Test (ETT)
	Blood pressure, 12-lead ECG
8:50 AM	Start Treadmill ETT (Standard Bruce Protocol, max time=21 minutes)
	Stage 1 (1.7 mph, 10% grade, 3 mins)
8:53 AM	(if necessary) Begin Stage 2 (2.5 mph, 12% grade, 3 mins)
8:56 AM	(if necessary) Begin Stage 3 (3.4 mph, 14% grade, 3 mins)
8:59 AM	(if necessary) Begin Stage 4 (4.2 mph, 16% grade, 3 mins)
9:02 AM	(if necessary) Begin Stage 5 (5.0 mph, 18% grade, 3 mins)
9:05 AM	(if necessary) Begin Stage 6 (5.5 mph, 20% grade, 3 mins)
9:08 AM	(if necessary) Begin Stage 7 (6.0 mph, 22% grade, 3 mins)
+0:20 mins	Monitored rest recovery period
+2:00 hours	Unmonitored rest period. Patient remains on the CRC
Part 2	Atropine Pre-treatment Treadmill Exercise Tolerance Test
11:00 AM	Blood pressure, 12-lead ECG
11:05 AM	Give Atropine (0.04 mg/kg up to max of 3 mg I.V.)
	Start ETT (Standard Bruce Protocol, max time=21 minutes)
	Stage 1 (1.7 mph, 10% grade, 3 mins)
11:08 AM	(if necessary) Begin Stage 2 (2.5 mph, 12% grade, 3 mins)

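### The plan sets no ectopy condition in Section 6 for ending monitoring after the baseline exercise test, and does not enforce its statement about two uneventful prior tests

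*Combined protocol and SAP*

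**What the plan says.** **Monitoring.** Section 7.0 commits to a period with an ectopy end point: "participants will be observed with continuous cardiac monitoring for 20 minutes following ETT, or until ventricular ectopy has returned to baseline (whichever is longer"). The paragraph opens with "Risks associated with Atropine include proarrhythmia", and the sentence is offered as the way to manage that risk.

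For the baseline ETT, the Section 6.0 table gives 20 minutes of monitored recovery and then 2 hours described as "Unmonitored rest period. Patient remains on the CRC". The narrative under Exercise Tolerance Test gives the same sequence and calls the 2 hours unsupervised. For the atropine ETT, the table gives 20 minutes of monitored recovery and discharge after 4 hours of observation, with removal of the monitor listed after that. Ectopy is not mentioned as a condition in either place.

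**Prior tests.** Section 7.0 also states: "All patients included in our study have successfully completed a minimum of two exercise stress tests with no adverse events". It then says "Unexpected findings are cardiac arrest, ICD shock, or death". Section 4.0 has four inclusion and three exclusion criteria, none on stress-test history. Before Day 1, the Section 6.0 table lists only "Patient recruited in clinic or by phone" and continuation of usual medication.

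**The concern.** The risk section describes two protections that the operational sections do not carry. Staff on the day will work from the Section 6.0 table. Followed as written, it moves a patient from monitored to unmonitored rest at 20 minutes, even if exercise-provoked ectopy has not settled. The disease carries a risk of sudden death, and Section 7.0 lists cardiac arrest and death among the unexpected findings. The sponsor's hypothesis (Section 2.0) is that exercise without atropine produces more ectopy than exercise with it. The test expected to be the more arrhythmic is therefore the one followed by unmonitored rest.

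The second gap concerns who enters. The risk assessment leans on a history of uneventful stress tests. A patient with no such test, or with a serious event during one, is not excluded by any written history criterion.

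**Working it through.** No statistical figure is at issue, so the check sets the sections side by side and adds clock times.

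**1. What follows each test**

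| | After baseline ETT | After atropine ETT |
|---|---|---|
| Monitored recovery (Section 6.0) | 20 min, fixed | 20 min, fixed |
| Next period (Section 6.0) | 2 h, expressly unmonitored | 4 h observation, monitor removed afterwards |
| Ectopy condition in Section 6.0 | none | none |
| Section 7.0 rule | applies only if the unqualified term ETT covers both tests | applies on any reading |
| Practical gap | yes | no |

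The condition is missing from Section 6.0 for both tests, but the omission has a consequence only in the baseline column.

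**2. Room in the timetable.** The baseline ETT starts at 8:50 and lasts at most 21 minutes.
- End of exercise at the maximum: 8:50 + 21 min = 9:11.
- End of monitored recovery: 9:11 + 20 min = 9:31.
- End of 2 h unmonitored rest: 9:31 + 120 min = 11:31, which is 31 minutes after the printed Part 2 start of 11:00.
- Counting back: 11:00 − 140 min = 8:40, before the baseline ETT begins.
- If the 2 hours are taken to include the 20 minutes, as the General Approach paragraph could be read: 9:11 + 120 min = 11:11, still after 11:00.

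The printed times thus leave no room for longer monitoring after a full-length baseline test. The amendment has to allow a later Part 2 start.

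**3. Effect of longer monitoring on the primary count.** Section 6.0 defines the primary comparison as ectopic beats during exercise and recovery, paired within patient. Section 10.0 analyses it with the Wilcoxon signed-rank test. Let a patient have ectopy at r beats per minute for t minutes beyond minute 20 of baseline recovery. If the count follows the monitoring, the baseline total rises by r × t, and so does the difference baseline minus atropine. That would favour atropine solely because one recording was longer. Counting over the same fixed window in both tests makes this contribution zero. The documents give neither r nor t, so no size is attached.

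**4. Prior stress tests**
- Inclusion (4): age, consent, clinical diagnosis, ability to exercise on a treadmill. None concerns earlier tests.
- Exclusion (3): treadmill contraindications, pregnancy, investigator judgement about an ongoing condition. None requires earlier tests, and a past event during a test is not clearly an ongoing condition.
- Result: 0 of 4 + 3 = 7 criteria, and no step in Section 6.0, require or check the history stated in Section 7.0.

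**The case against.** **The Section 7.0 rule is about atropine.** This is the strongest counter-argument, and most of it stands. The sentence manages a risk that the paragraph attributes to atropine, and no atropine has been given at the baseline ETT. A reader might infer that Section 6.0 contradicts a commitment already made for the baseline test. The documents do not establish that; they leave the scope open. The case for the change does not need it, because a fixed 20 minutes followed by unmonitored rest is the weaker rule on either reading.

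**Section 7.0 is itself protocol text.** If it covers both tests, careful staff would apply it. That is fair, but the table they follow gives no such instruction and no spare time.

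**Other safeguards exist.** Usual therapy continues, exercise has stopping rules, the patient stays at the research centre, blood pressure and a 12-lead ECG are repeated before atropine, and Section 9.0 allows withdrawal in the patient's interest. These reduce the risk. None sets a condition for ending monitoring after the baseline ETT.

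**ICD settings.** A reader might infer that ICD patients are less protected during the unmonitored rest, because the table includes "Reprogram therapy detection zones if needed" before the first test and restores settings at the end. The documents do not support this as an argument here. Changes are conditional, their direction is not given, and the proposed fix would not alter the interval.

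**Prior tests.** The sentence may simply describe a known group of patients. That is possible, though the document does not say so. It is why qualifying the sentence is an acceptable remedy.

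**Conclusion.** The point holds as a clarification that brings a cheap gain in safety. Section 7.0 does not say which ETT its monitoring rule covers, and Section 6.0 repeats the rule for neither. The consequence is confined to the baseline ETT, where 20 minutes of monitoring is followed by 120 minutes without it, regardless of ectopy. It would be wrong to extend the point to the atropine ETT.

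The size of the harm is unknown: the plan does not say how many patients have ectopy beyond 20 minutes. A reader might take the large unmonitored part of the scheduled rest as a measure of risk. It is only a ratio of scheduled times and says nothing about how many patients are exposed.

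The prior-test point is secondary. Absence of the requirement is confirmed for Sections 4.0 and 6.0 only, because Appendix A (the study procedure calendar) was not available. A reader might infer that patients with eventful tests will be enrolled. The documents show only that the written criteria do not prevent it.

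Neither point affects the type I error or power. The verdict assumes that a return to baseline means a return to the pre-exercise level of ectopy, which the plan does not define.

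**What to change.** 1. **Section 6.0, table and narrative, after the baseline ETT.** State that monitoring lasts 20 minutes or until ventricular ectopy is back to baseline, whichever is longer, and that unmonitored rest starts only then. Let the Part 2 start move later when needed.
2. **Primary count.** Fix one recovery window for counting ectopic beats, for example 20 minutes, and apply it to both tests whatever the length of monitoring.
3. **Prior stress tests, one of two options.**
   - Add a criterion checked against the medical record before Day 1: at least two prior exercise tests, and no prior exercise test with cardiac arrest, ICD shock, syncope or sustained ventricular tachycardia. Provoked ectopy is allowed, and the investigator should confirm the event list. Both clauses are needed, because requiring two clean tests alone would admit a patient with a third, eventful one. Absence of any adverse event should not be the criterion: the Section 8.0 definition includes "Patient / subject deterioration due to the primary illness", which could exclude patients whose test provoked the arrhythmia under study.
   - Or, if no requirement is intended, qualify the Section 7.0 sentence.

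**Cost.** Text changes and, under the first option in item 3, a record check; no new procedure. Patients with persisting ectopy get a longer day (already about 8 hours) and a variable rest interval between tests. A new criterion may make some patients ineligible. Qualifying the sentence excludes no one.

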9.0 Study Withdrawal/Discontinuation

Participants may withdraw from the study at any time by informing the study staff verbally or in writing. If an individual withdraws their consent, we will withdraw the participant. Contact information for the PI and study staff will be made available to the participant upon enrollment in the consent document. Any remaining biological samples and data will be destroyed. Any data or biological samples that have been used for research prior to their withdrawal request will not be withdrawn and destroyed.

A participant may be withdrawn from the study by the PI if any of the following occurs:

Protocol Version #: 7 Protocol Date: 6/28/2016

- i. A procedural complication occurs prior to completion of the study protocol that requires the study procedure to be aborted, or precludes collection of study data.
- ii. The patient becomes hemodynamically unstable for any other reason that requires the study procedure to be cancelled prior to completion of the study protocol, or precludes the collection of study data
- iii. The primary operator determines it is in the patient's best interest to forego completion of the study protocol

10.0 Statistical Considerations

Baseline clinical characteristics will be described using frequency and percentage for dichotomous variables and median with interquartile range for continuous variables. The design of this study is a crossover trial between "no treatment" and "atropine treatment". The primary outcome variable is a continuous variable measuring the number of beats of ventricular ectopy. The null hypothesis is that no difference exists between the "no treatment" and "atropine treatment" interventions in the number of beats of ventricular ectopy. The primary analysis will use a Wilcoxon-signed ranked test. A P-value <0.05 will be used to reject the null hypothesis. A secondary outcome will be measurement of complex ventricular ectopy defined as couplets or greater. Comparisons will be made between the "no treatment" and "atropine treatment" and percentage to reject the null hypothesis. A secondary outcome will be measurement of complex ventricular ectopy defined as couplets or greater. Comparisons will be made between the "no treatment" and "atropine treatment" groups using: 1) the number of runs of complex ventricular ectopy (continuous variable) using the Wilcoxon-signed ranked test; and 2) the presence of complex ventricular ectopy (yes/no) using McNemar's test. As a pilot study, we may be underpowered to detect our primary analysis, but valuable data regarding the effect size and confidence intervals will be obtained to provide sample size estimations for subsequent larger scale clinical trials.

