11:11 AM	(if necessary) Begin Stage 3 (3.4 mph, 14% grade, 3 mins)
11:14 AM	(if necessary) Begin Stage 4 (4.2 mph, 16% grade, 3 mins)
11:17 AM	(if necessary) Begin Stage 5 (5.0 mph, 18% grade, 3 mins)
11:20 AM	(if necessary) Begin Stage 6 (5.5 mph, 20% grade, 3 mins)
11:23 AM	(if necessary) Begin Stage 7 (6.0 mph, 22% grade, 3 mins)
+0:20 mins	Monitored rest recovery period
Find of	
End of Study	
+4:00 hours	Discharge home after 4 hours of observation
	Erase arrhythmia counters on device and reprogram any changes made to therapy
	detection zones
	Disconnect from monitor and remove electrodes
	Remove peripheral I.V.
	Discharged from CRC

Exercise Tolerance Test (ETT)

The ETT protocol is adapted from the clinical protocol used at the Vanderbilt Heart and Vascular Institute. The participant will be asked to not eat or drink for 4 hours prior to each session, except for a small amount of water used to take necessary meds. He/she will be instructed to take all medication as prescribed prior to the test. Participants will be instructed to wear clothing and shoes appropriate for exercising on a treadmill. An IV will be placed in order to deliver medication during the testing. For a patient with an ICD, the patient's ICD will be interrogated, and reprogrammed if necessary. Electrodes will be placed for ETT.

The patient will be instructed to stand on the treadmill, and will be asked to begin walking on the treadmill using Bruce protocol. The patient will be encouraged to maintain a minimum heart rate of 85% of his/her age predicted maximum. He/She will be encouraged to walk/run until the end of their comfort zone unless the supervising professional terminates the test before then. The exercise portion of the study is planned to last a maximum of 21 minutes per session. The two sessions will be separated by a 20 minute

supervised rest period followed by a 2 hour unsupervised rest period where the patient will be asked to remain at the CRC. After the second exercise session, a 4+ hour observation period will begin. For a patient with an ICD, any changes to ICD settings will be reprogrammed to previous settings. The patient will be disconnected from monitors and electrodes, and the peripheral IV will be removed. In total, the total time commitment is approximately 8 consecutive hours. The medication used during the testing may cause discomfort or an unpleasant sensation.

Exercise will be terminated prior to the end of the test under the following circumstances:

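### Does the primary signed-rank test need a written analysis set for tests stopped early and participants withdrawn by the PI?

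*Combined protocol and SAP*

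**What the plan says.** Section 6.0 of the combined protocol and SAP defines the comparison: "The primary analysis will be a paired comparison of the number of ventricular ectopic beats recorded during exercise (and recovery) at baseline" and after atropine. The tests are close together: "Both ETTs will be performed on the same day with two hours of rest scheduled between ETTs". Atropine always comes second, because Section 5.0 makes the study non-randomised. Section 10.0 names the method: "The primary analysis will use a Wilcoxon-signed ranked test", with a 0.05 threshold. It gives no sample size, analysis population or rule for incomplete data.

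Exercise is symptom-limited: "He/She will be encouraged to walk/run until the end of their comfort zone unless the supervising professional terminates the test before then". Section 6.0 also lists reasons for ending a test before its planned end. These range from sustained ventricular tachycardia to fatigue and inability to exercise. ECG is recorded through both exercise and recovery.

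Section 9.0 covers withdrawal. It says "A participant may be withdrawn from the study by the PI if any of the following occurs". One ground is a complication that "requires the study procedure to be aborted, or precludes collection of study data"; another is the operator's view that it is in the patient's "best interest to forego completion of the study protocol". The sentence "Any remaining biological samples and data will be destroyed" sits with withdrawal of consent and does not define who is analysed.

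**The concern.** A participant who never has the second test drops out of a paired analysis automatically. The doubtful cases have two tracings: a test cut short, or a participant withdrawn by the PI after recording began. The first ground in Section 9.0 joins an aborted procedure and lost data with an 'or', so a withdrawn participant may still have usable counts. The operator-judgement ground is not tied to missing data at all.

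Some of this could be related to the outcome. Sustained ventricular tachycardia ends a test, and a shortened test can yield a lower raw count. The study is open-label, ectopy is visible during the test, and no passage describes blinded reading or fixing the pairs beforehand.

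The pilot's stated product is an effect size and confidence interval for planning later trials. With few participants, one pair can move both the p-value and the estimate.

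**Working it through.** **Inputs.** From the document: paired counts, signed-rank test, 0.05 threshold. Sidedness is not stated; the null of no difference is read as two-sided. Sample size, SD and stopping rate are not given, so every value for them below is assumed. There is no planned figure to reproduce.

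**Exact test.** With n non-zero, untied differences and rank sum W in the minority direction, the two-sided p is 2 × (number of subsets of ranks 1 to n with sum ≤ W) / 2^n.

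- 8 pairs, one adverse with the largest change, W = 8: subsets with sums 0 to 8 number 1+1+1+2+2+3+4+5+6 = 25, so p = 50/256 = 0.195.
- That pair left out, n = 7, W = 0: p = 2/128 = 0.016.
- 8 pairs, one adverse with the smallest change, W = 1: p = 4/256 = 0.016, the same as leaving it out.
- 6 pairs all lower: p = 2/64 = 0.031. One left out: 2/32 = 0.0625.

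So one pair can matter, but how much depends on its rank.

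**Bound for deliberate selection.** Under no effect (40,000 runs each for n = 8, 10, 12, 15, 20; normal differences), always dropping the pair most adverse to atropine raises the two-sided error from about 3.8-5.0% to about 8.0-9.9%. Nothing in the plan licenses such a rule.

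**Three candidate sets.** A: everyone with both counts. B: only pairs with neither test stopped early. C: pairs whose atropine test was not stopped. Assumptions: n = 8 to 20, log-ratio SD 0.6, the same stop rule in both tests with odds of stopping tripled per SD of log count, and baseline stoppers going on to the second test.

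False benefit under no effect, with 14% of tests stopped:

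| Set | False benefit |
|---|---|
| A | 1.9-2.6% |
| B | 1.4-2.3% |
| C | 2.3-3.4% |
| Most favourable of the three | 3.1-4.9% |
| Most favourable of A and B only | 2.8-3.5% |

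The most favourable of the three gives 2.6-3.5% at 5% stopped and 2.3-2.8% at about 2% stopped.

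With a true ratio of 0.6, the three sets disagree on p < 0.05 in 17-27% of trials at 14% stopped, 7-12% at 5% and 3-4.5% at about 2%. Much of this is lost power rather than bias: at the highest stopping rate, power is 42-88% for A and 28-77% for B.

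**Which set the text supports.** Section 6.0 asks for a paired comparison of recorded beats, and Section 10.0 for a test that uses every complete pair. That is A. No passage excludes a recorded test because it ended early. C, which would drop early-stopped atropine tests but keep early-stopped baseline tests, has no basis in the text.

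**Whether B is usable.** Participants exercise to their own limit, up to 21 minutes, and fatigue and inability to exercise are on the list of reasons for ending early. Read literally, an ordinary symptom-limited test is an early stop, and B could be nearly empty.

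**The case for a change.** The best case for a change is that it is cheap. Three sentences and a listing would settle the primary set before any tracing is read, in a study where one pair can decide significance and no one is blinded. Section 5.0 adds that atropine has increased voluntary withdrawal in earlier studies. With atropine always second, that attrition is tied to treatment, and a reader will want to know who had only one test and why.

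The silence is real, and a pilot label does not excuse it. Listing one-test participants, early terminations and withdrawals by test and reason is good reporting, and can be done without amending the analysis.

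The rest is weaker. That the choice would be made after the counts are seen is an inference; the plan does not say so. Writing down A would not remove bias either. If no baseline stopper goes on to atropine and stopped tests carry half the count, A itself gives 3.0-5.5% false benefit at 14% stopped, much the same as the 3.1-4.9% from free choice in the other scenario. A sensitivity analysis on B would first need a definition of early stopping that separates safety or technical terminations from ordinary symptom-limited completion. Without that, it would bring in a new ambiguity.

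**Conclusion.** This is a gap that analysts fill sensibly, and no change to the plan is needed. Read together, Sections 6.0 and 10.0 lead to one primary set: all participants with a count from both tests, as recorded, including tests ended early and any pair recorded before a PI withdrawal. Stating it would leave the primary result as it is.

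The possible effect runs from none (the smallest-rank example) to a p-value crossing 0.05 (0.195 against 0.016). Both ends rest on assumed data. In the simulations the cost of free choice shrinks to near the nominal 2.5% per direction when about 2% of tests are stopped. Section 7.0 suggests stops may be few, since it says every participant has already been through at least two stress tests without an adverse event.

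The conclusion depends on the analysts taking that plain reading. If the report excluded recorded pairs without explanation, a reader would be right to ask for the result with them included.
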